4.4.2.4.2 Supportive Analyses

If there is at least 10% difference in the overall number of subjects between PP and mITT Populations, a summary and statistical analysis of each of the DHEQ-48 Score endpoint will be presented for the PP Population in (Table 14.2.4.1.2 and 14.2.5.1-8.1.2 for Section 1 and Section 2 respectively) and (Table 14.2.4.2.2 and 14.2.5.1-8.2.2 for Section 1 and Section 2 respectively), respectively for summary table and analysis table. In addition, DHEQ-48 score (Figure 14.2.3.2 and Figure 14.2.2.3-10.2 for Section 1 and Section 2 respectively) for each mentioned endpoint at each time point will be plotted by study product in for all subjects in PP Population.

A decision on whether a PP analysis will be performed will be made prior to study unblinding (release of the randomization codes).

[figure not shown]
4.4.3 Exploratory Efficacy Variables

Satisfaction with Treatment using Numeric Rating Scale:

At the end of the study (Visit 7), subjects will be asked to rate their level of satisfaction with their allocated study product using a NRS. The NRS is an 11-point ordinal scale used to assess the subject's satisfaction with the product's overall management of their DH. The scale ranges from 0 (completely dissatisfied) to 10 (completely satisfied), with higher scores indicative of greater satisfaction (van Berckel, 2017): See example below:

Subjects will be asked to record the numeric value on the segmented scale that best describes their level of satisfaction after 8 weeks twice daily use and indicate why they selected a particular score in answer to the question 'Please give more details on why you are satisfied or dissatisfied with the product' (free text response).

Figure 4-1 Numerical Rating Scale (0 to 10)

4.4.3.1 Satisfaction NRS Score

Descriptive statistics (n, mean, SD, standard error [SE], median, minimum, and maximum) will be presented for NRS Score at Day 56 in Table 14.2.5.9.2 for all subjects in mITT population by study product.

Also, summary of the number of subjects (%) reporting at each level of the NRS and the cumulative number of subjects (%) reporting at each level or higher at Day 56 will be presented in Table 14.2.5.9.1 by study product.

4.4.3.1.1 Statistical Hypothesis, Model and Method of Analysis

No formal statistical analysis is planned for assessment of NRS endpoint.

4.4.4 Handling of Missing Values/Censoring/Discontinuations

Missing data will not be replaced or imputed. Subjects who withdraw from the study prematurely will be included in the statistical analyses up to the point of discontinuation.

The use of MMRM analyses account for missing data assuming a missing at random assumption, i.e., there is a systematic relationship between the propensity of missing values and the observed data, but not the missing data.

It is therefore assumed that a subject with missing data at one post-Baseline assessment visit would have obtained a similar efficacy result at that visit compared to a subject using the same study product with similar non-missing results at other timepoints (Baseline and the other post-Baseline assessment visits). Sensitivity analyses may be added to the SAP prior to unblinding in case of high drop-out rates and/or exclusion from PP analyses.

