8.2.5 Visit 6 / Day 28 (± 2 days)

Repeat procedures, clinical examination, DH assessments and supervised brushing as described for Visit 3 / Day 3.

In addition, prior to commencing the clinical examination/assessments, each subject will independently (without supervision) complete a hard copy of the DHEQ-48 (source), Section 1 Questions 7-9 and Section 2 all questions ([Appendix 15.2](#)). Subject responses will be later transcribed into the eCRF.

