9.2.1 Dentine Hypersensitivity Experience Questionnaire (DHEQ-48)

The [DHEQ-48](#) is a condition-specific measure of OHrQoL in relation to DH ([Boiko, 2010](#)) that has been previously validated in longitudinal studies and shown to be responsive to treatment ([Baker, 2014](#)). The DHEQ total score can be broken down into 5 separate ‘domain’ scores to provide a more granular understanding of the specific areas of improvement subjects experience in their OHrQOL.

- **Restrictions:** Derived from participant responses to Section 2, Q1-4 ('*the ways in which any sensations in your teeth affect you in your daily life*').
- **Adaptation:** Derived from participant responses to Section 2, Q5-16 ('*the ways in which the sensations in your teeth have forced you to change things in your daily life*'; '*things you do in your daily life to avoid experiencing the sensations in your teeth*').
- **Social Impact:** Derived from participant responses to Section 2, Q17-21 ('*the way the sensations affect you when you are with other people or in certain situations*').
- **Emotional Impact:** Derived from participant responses to Section 2, Q22-29 ('*the way the sensations in your teeth make you feel*').
- **Identity:** Derived from participant responses to Section 2, Q30-34 ('*what the sensations in your teeth mean for you*').

The DHEQ also provides specific information on how much the sensations in the participant's teeth affect their life overall:

- **Global Oral Health:** Derived from participant response to Section 2, Q35 ('*rate the health of your mouth, teeth and gums*').
- **Effect on Life Overall:** Derived from participant responses to Section 2, Q36-39 (impact of DH on overall quality of life).

Subjects will independently (unsupervised) complete a hard copy of the DHEQ-48 ([Appendix 15.2](#)) at Baseline (Visit 2), Day 28 (Visit 6) and Day 56 (Visit 7), prior to any clinical examinations and assessments.

- **Baseline:** Complete Section 1 and Section 2 (i.e., all questions in both sections).
- **Day 28 & Day 56:** Complete Section 1 Questions 7-9 only, and Section 2 all questions.

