11.3 Processing Subject Reported Outcomes

Subject reported outcomes will be recorded in paper-based diaries and in questionnaires (DHEQ-48 and NRS) for later transcription into the eCRF.

Source documents recording subject-reported outcomes will be reviewed by the investigator staff and the study monitor to ensure the data, and any potential AEs or concomitant medications reported in these documents, are accurately transcribed into the eCRF.

Subject reported outcomes classed as source data will be retained by the investigator; true/certified copies may be sent to the sponsor or a third-party vendor, as required. To protect subject privacy, no PI (including subject name, initials or birth date) is to be recorded in any subject reported outcome source document that will be forwarded to the sponsor or a third-party vendor.

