|  Hard foods (10) |  Sticky foods (11) |  Tooth Whitening Products (12) |
|  Cold air (13) |  Ice Cream (14) |  Metals touching my teeth (15) |
|  Other (Please Specify) (16) | | |
|  None (17) | | |

5) How often do you have any **sensations**? (tick only one response)

[figure not shown]
- Several times a day (7)
- Once a day (6)
- Several times a week (5)
- Once a week (4)
- Several times a month (3)
- Once a month (2)
- Less than once a month (1)
- Never (0)

6) If you have any **sensations**, on average how long do these sensations last? (tick only one response)

[figure not shown]
- A few seconds (5)
- About a minute (4)
- Several minutes (3)
- About half an hour (2)
- Longer than half an hour (Please specify) (1)
- Don't have them (0)

The following questions are about your sensitive teeth, and the impact it has on your everyday life.

[figure not shown]
7) On a scale of 1 to 10 how intense are the sensations? (Please circle your answer)

8) On a scale of 1 to 10 how bothered are you by any sensations? (Please circle your answer)

9) On a scale of 1 to 10 how well can you tolerate sensations? (Please circle your answer)

Property of Haleon- Confidential

May not be used, divulged, published or otherwise disclosed without the consent of Haleon

CCI

Clinical Protocol Template v10.0

Page 87 of 92

SECTION TWO

The following questions are about **the ways in which any sensations in your teeth affect you in your daily life**. Thinking about yourself *over the last month* to what extent would you agree or disagree with the following statements (Please tick only one response for each question).

| | Strongly agree (7) | Agree (6) | Agree a little (5) | Neither agree nor disagree (4) | Disagree a little (3) | Disagree (2) | Strongly disagree (1) |
|---|--------------------------|--------------------------|--------------------------|--------------------------------|--------------------------|--------------------------|--------------------------|
| 1) Having sensations in my teeth takes a lot of the pleasure out of eating and drinking. |  |  |  |  |  |  |  |

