3.1 Baseline Definition

For all endpoints, the baseline value will be the Day 0 (Visit 2) pre-treatment assessment with a non-missing value.

Unless otherwise stated, if baseline data is missing no derivation will be performed and the baseline value will be set to missing.

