1. DHEQ Total Score (sum of Q1-34)
2. DHEQ Restrictions Domain score (sum of Q1-4)

-
3. DHEQ Adaptation Domain score (sum of Q5-16)
 4. DHEQ Social Impact Domain score (sum of Q17-21)
 5. DHEQ Emotional Impact Domain score (sum of Q22-29)
 6. DHEQ Identity Domain score (sum of Q30-34)
 7. DHEQ Global Oral Health Score (Q35)
 8. DHEQ Effect on Life Overall Score (sum of Q36-Q39)

Change from Baseline will be calculated at the subject-level first then mean change from Baseline will be calculated for each DHEQ endpoint (mentioned above) across all subjects.

Descriptive statistics (n, mean, SD, standard error [SE], median, minimum, and maximum) will be presented for each DHEQ-48 endpoint (mentioned above) at each assessment time point in Table 14.2.4.1.1 and 14.2.5.1-8.1.1, for Section 1 and Section 2 respectively and for all subjects in mITT population by study product. Raw means (\pm SE) for each DHEQ endpoint, and the individual DHEQ questions, at each assessment will be plotted by study product in Figure 14.2.3.1 and Figure 14.2.2.3-10.1, for Section 1 and Section 2 respectively and for all subjects in mITT population.

Individual DHEQ endpoint data for each endpoint (mentioned above) will be listed for each subject by visit and study product group in Listing 16.2.6.5, 16.2.6.6.1-7, for Section 1 and Section 2 respectively, for all randomized subjects.

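### With DHEQ scores defined as plain sums and imputation ruled out, one blank item voids the whole score, and a blank at Baseline removes the subject from that endpoint's model

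*SAP*

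**What the plan says.** SAP 4.4.4 states: "Missing data will not be replaced or imputed". The rest of that section deals with withdrawals and with a missed post-Baseline visit. It does not mention single questionnaire items, either to include or to exempt them.

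SAP 4.4.2.4, like protocol 12.3.2, defines the summed DHEQ endpoints only by their item ranges, for example "DHEQ Total Score (sum of Q1-34" and "DHEQ Restrictions Domain score (sum of Q1-4". The other domains have 12, 5, 8 and 5 items, and Effect on Life Overall has 4 (Q36-39). Neither document gives a minimum number of answered items, a prorating rule or any instruction for a partly completed form.

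On collection, protocol 9.2.1 says: "Subjects will independently (unsupervised) complete a hard copy of the DHEQ-48". This applies at Baseline, Day 28 and Day 56. Protocol 11.3 says source documents for subject-reported outcomes "will be reviewed by the investigator staff and the study monitor to ensure the data" are transcribed accurately. No check for blank items while the subject is still on site is described.

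For Baseline, SAP 3.1 says: "if baseline data is missing no derivation will be performed and the baseline value will be set to missing". SAP 4.4.2.4.1 then uses the Baseline DHEQ score as the covariate in the MMRM for change.

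**The concern.** A sum with a missing term that may not be filled in is itself missing. One blank among 34 items therefore discards 33 valid answers. The loss grows with the number of items, so the Total Score is hit hardest. A blank at Baseline costs more than a blank at follow-up, because without the covariate none of the subject's follow-up scores can enter that model.

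The text also leaves room for a second, worse coding. A routine that skips missing values when it adds would count the blank as 0, although the lowest answer on the items shown in protocol Appendix 15.2 is 1. Those items are worded so that agreement (7) is the bad end, for example "Having sensations in my teeth takes a lot of the pleasure out of eating and drinking". A blank counted as 0 at Day 28 or Day 56 would look like improvement, and one at Baseline would hide improvement. Two programmers working from this SAP could produce different secondary results. At stake are completeness and precision for a set of listed secondary endpoints, and a scoring choice that might otherwise be made after unblinding.

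**Working it through.** **Plan's own figure.** The documents give no figure for DHEQ completeness. Their one sizing calculation (105 per group, difference 0.25, SD 0.55, two-sided 5%, Schiff score at Day 3) reproduces: exact noncentral-t power is 0.906 against the stated 90%. It does not enter this point.

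**Inputs.**
- Items per score: 34 (Total); 4, 12, 5, 8 and 5 (domains); 4 (Effect on Life Overall). From SAP 4.4.2.4.
- DHEQ visits: Baseline, Day 28, Day 56. From protocol 9.2.1.
- Item scale: 1 to 7 on the items I can see in Appendix 15.2 (Q1-33).
- Blank rate q per item: **assumed**, 0.1% to 2%, independent across items and visits. All three visits are taken as attended, so dropout comes on top.

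**Step 1: chance that a k-item form is complete.** p = (1 − q)^k.

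**Step 2: chance that a subject contributes to the MMRM.** The Baseline form must be complete, and at least one of the two follow-up forms: p × [1 − (1 − p)²].

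Example, Total at q = 1%: p = 0.99^34 = 0.711. Contribution = 0.711 × (1 − 0.289²) = 0.651.

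| q per item | p, Total (34 items) | Contributes, Total | Contributes, Adaptation (12 items) | Contributes, Restrictions (4 items) |
|---|---|---|---|---|
| 0.1% | 0.967 | 97% | 99% | 100% (99.6%) |
| 0.25% | 0.918 | 91% | 97% | 99% |
| 0.5% | 0.843 | 82% | 94% | 98% |
| 1% | 0.711 | 65% | 87% | 96% |
| 2% | 0.503 | 38% | 75% | 92% |

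**Step 3: size of the error if a blank were summed as 0.** A k-item score on a 1-7 scale has a span of 7k − k = 6k. One blank lowers the score by its true value, 1 to 7 points.
- Restrictions (k = 4, span 24): 1/24 to 7/24, or 4.2% to 29.2% of the span.
- Adaptation (k = 12, span 72): 1.4% to 9.7%.
- Total (k = 34, span 204, assuming Q34 is also scored 1-7): 0.5% to 3.4%.

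I give no figure for Effect on Life Overall, because the response options for Q36-39 are not in the text I have.

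**Step 4: effect of half-answered proration.** The Total is lost only if some domain has fewer than half its items answered: at least 3 blanks of 4, 3 of 5, 5 of 8 or 7 of 12. At q = 2% the binomial chance that all five domains pass is 0.9998, so contribution to the Total Score model rises from 38% to over 99.9% under the same assumptions.

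**The case against.** The strongest reply is that the 4.4.4 sentence is about missed visits. Everything around it concerns withdrawal and a missing post-Baseline visit, so it may never have been meant for single items. That is plausible, but the sentence is unqualified and no other text governs items. If it does not apply, there is simply no rule.

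A reader might infer that the SAP scores a blank as improvement. It does not. Counting a blank as 0 is in effect a replacement, which 4.4.4 forbids; the SAP never prescribes it; and the bias would be toward improvement only for post-Baseline blanks. Equal blank rates at all visits would largely cancel in the mean change. The point is that the SAP should close off this coding, not that it adopts it.

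A reader might also take the loss to be the chance that Baseline and one given follow-up are both complete: (1 − q)^68, about 50% at q = 1% and 25% at 2%. That overstates the loss, because the MMRM keeps a subject who has either follow-up score. Nor do the documents support a claim that much of the sample will be lost, or that those kept are the careful form-fillers. No blank rate is given, and independence sits at the high end of loss.

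Existing controls also bear on the rate. Forms are completed on site, source documents are reviewed (protocol 11.3), edit checks and queries apply (11.2.1), and the investigator certifies the data as complete (11.1). None is a stated blank-item check before the subject leaves, and 5 days are allowed for transcription. These controls should make blanks rarer, but they do not say how to score one. The instrument's own scoring guidance may contain a rule; neither document cites one.

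**Conclusion.** The point holds as a scoring gap of minor consequence. Read literally, the no-imputation sentence and the plain sums void a DHEQ score for one blank, and a voided Baseline score removes the subject from that endpoint's MMRM. Under assumed independent blanks of 0.1% to 2% per item, contribution to the Total Score model runs from about 97% down to 38%. Shorter scores lose much less, and clustered blanks would lose fewer.

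A reader might go on to infer a threat to the trial's conclusion; the documents do not support that. The DHEQ objective is descriptive, the scores sit outside the sequential testing strategy, and the planned test is post-Baseline against Baseline within each group. Study success rests on the Schiff score at Day 56. Only the DHEQ adjusted means, confidence intervals and p-values are exposed.

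**What to change.** Add to SAP 4.4.2.4:
- If at least half the items of a domain, or of Effect on Life Overall (Q36-39), are answered, the score is the mean of the answered items times the number of items in that score; otherwise it is missing. In practice this means at least 2 of 4, 3 of 5, 4 of 8 or 6 of 12.
- The Total is the sum of the five domain scores and is missing if any domain is missing.
- Blank items are never summed as 0.
- If the instrument's own scoring guidance gives an item-missing rule, use and cite that instead.

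In SAP 4.4.4, state that the no-imputation rule applies to missed visits and wholly missing scores. These changes should be made before unblinding. The existing provision for late additions is tied to high dropout or per-protocol exclusions, so blank items would not trigger it.

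At the site, ask the staff who already review the forms to check for blanks before the subject leaves, preferably before the clinical assessments start, since the protocol wants the questionnaire completed first.

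The cost is a few sentences, a few lines of code and a short check at three visits. The downside is that proration assumes a blank resembles the subject's other answers in the same domain. The half-answered threshold is a working choice, not one taken from the documents.

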4.5 Analysis of Safety

The safety profile of the study products will be assessed with respect to AEs or incidents and OST/OHT abnormalities in oral health study.

4.5.1 Adverse Events and Serious Adverse Events

All AEs will be reviewed by the Clinical Research Scientist or Designee prior to database lock and will be coded to a system organ class (SOC) and preferred term (PT) using the Medical Dictionary for Regulatory Activities (MedDRA).

AEs will be classified as oral and non-oral on the AE page of eCRF.

Treatment emergent adverse events (TEAEs) are defined as new AEs that occur on or after the first study product use (if this date is missing a suitable alternative will be used e.g., date of randomization). AEs with an onset date/time prior to the first study product use will be considered as non-treatment emergent.

The following summary tables and listings will be presented by study product.

-
- Table of TEAEs by SOC and PT (Table 14.3.1.1).
 - Table of TEAEs by Oral/Non-Oral and PT (Table 14.3.1.2)
 - Table of treatment related TEAEs by SOC and PT (Table 14.3.1.3)
 - Table of treatment related TEAEs by Oral/Non-Oral and PT (Table 14.3.1.4)
 - Listing of all AEs (Listing 16.2.7.1 for safety population)
 - Listing of deaths (Listing 14.3.2.1)
 - Listing of non-fatal SAEs (Listing 14.3.2.2)
 - Listing of TEAEs leading to study or drug discontinuation (Listing 14.3.2.3)
 - Listing of TEAEs classified as Oral (Listing 14.3.2.4)

In the event that there is nothing to report, a null table or listing will be produced.

All incidents will be listed in Listing 16.2.7.2. In the event that there is nothing to report, a null listing will be produced.

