At Screening (Visit 1), following provision of written informed consent, suitability to participate will be reviewed against the protocol inclusion/exclusion criteria. Eligible subjects will enter an acclimatization period (14-28 days) prior to Baseline assessments during which

Property of Haleon- Confidential

May not be used, divulged, published or otherwise disclosed without the consent of Haleon

they will brush twice daily (morning and evening) with the acclimatization toothpaste (a different commercially available, regular fluoride toothpaste from the Reference Toothpaste). At Baseline (Visit 2), eligibility to continue will be assessed. Subjects who demonstrate the required qualifying levels of DH at Screening (Visit 1) and Baseline (Visit 2) will be randomized to study treatment and instructed to brush with their assigned investigational toothpaste twice daily (morning and evening) for the duration of the 8-week treatment period.

DH will be assessed at Screening (Visit 1), Baseline (Visit 2), and after 3-, 7-, 14-, 28- and 56-days treatment (Visits 3-7) using two independent clinical measures: (i) tactile threshold (g) following a tactile stimulus and (ii) Schiff sensitivity score following an evaporative (air) stimulus.

Oral health-related quality of life (OHRQoL) will be monitored over the treatment period using the Dentin Hypersensitivity Experience Questionnaire (DHEQ-48), completed by study subjects at Baseline (Visit 2), and after 28- and 56-days treatment (Visits 6 and 7). At the final visit (Day 56), subjects will rate their level of satisfaction with their assigned investigational toothpaste for the overall management of their DH, using a Numeric Rating Scale (NRS).

Safety and oral tolerability of the investigational toothpastes will be monitored over the 8-week usage period by review of treatment emergent adverse events (TEAEs).

Investigational Products:

| Description | Test Toothpaste | Reference Toothpaste (Negative Control) |
|-------------------------------|---|--|
| Name | 5.0 % w/w CSPS toothpaste | Regular fluoride toothpaste (Crest Cavity Protection*) |
| Master Formulation Code | CCI | N/A |
| Fluoride Level | 1040 parts per million (ppm) fluoride [†] | 1100 ppm fluoride [†] |
| Route of Administration | Topical Oral Use | |

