10.3 Time Period and Frequency for Collecting AE and SAE Information

All AEs, and therefore all SAEs, will be collected from immediately after a subject provides consent to participate in the study by the completion (signature) of the ICF until 5 days following the last administration of study product (or the last study procedure).

Medical occurrences that began before obtaining informed consent will be recorded in the Medical History/Current Medical Conditions section of the eCRF, not the AE section.

Details recorded by the subject in a diary or similar document that meet the definition of an AE must be discussed with the subjects and transcribed into the AE section of the eCRF.

All SAEs will be recorded and reported to the sponsor or designee immediately, and under no circumstance should this exceed 24 hours. The investigator will submit updated SAE data to the sponsor within 24 hours of it being available.

The investigator and their medically qualified designees are not obligated to actively seek AEs or SAEs after the conclusion of study participation. However, if the investigator or their medically qualified designee learns of an SAE, including a death, at any time after a subject has been discharged from the study, and they consider the event to be reasonably related to study product or study participation, they must promptly notify the sponsor.

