10.6 Follow-up of AEs and SAEs

After the initial AE/SAE report, the investigator or their medically qualified designee is required to proactively follow up with each subject and provide further information on the subject's condition, as available.

All AEs (non-serious and serious) should be followed until resolution, until the condition stabilizes, until the event is otherwise explained or until the subject is lost to follow-up.

The investigator or their medically qualified designee is obligated to perform or arrange for the conduct of supplemental measurements and/or evaluations as may be indicated (or as requested by the sponsor) to elucidate as fully as possible the nature and/or causality of the AE/SAE. These may include additional laboratory tests or investigations, histopathological examinations, or consultation with other healthcare professionals.

New or updated information will be recorded in the AE section of the eCRF and on the SAE form (as appropriate, subject to classification of the AE). The investigator or their medically qualified designee will submit any updated SAE data to the sponsor within 24 hours of receipt of the information.

The investigator and their medically qualified designees are not obligated to actively seek AEs or SAEs after the conclusion of study participation. However, if the investigator or their medically qualified designee learns of an SAE, including a death, at any time after a subject has been discharged from the study, and they consider the event to be reasonably related to study product or study participation, they must promptly notify the sponsor by emailing the information to the sponsor's Case Management Group mailbox **PPD** with the appropriate sponsor Study Manager in copy.

The investigator or their medically qualified designee will submit any updated SAE data to the sponsor within the designated reporting time frames.

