12.3.4 Safety Analyses

Safety analyses will be performed on the Safety population, according to investigational product received. AEs will be regarded as 'treatment emergent' if they occur on or after the first use of investigational product at Baseline (Visit 2). In the event of a missing start date, an AE will be assumed to be 'treatment emergent' unless the end date is prior to starting treatment. In case of misallocation, compared to the randomization schedule, TEAEs will be associated with the most recent study investigational received.

Each AE will be categorized as oral or non-oral by the investigator or medically qualified designee. All will be reviewed by the CRS and coded using the MedDRA prior to database lock and unblinding.

A listing of all AEs will be presented for all subjects in the Safety population with the following AE summaries (number of distinct AEs and frequency/proportion of subjects affected) presented by treatment group and overall:

- TEAEs
- TEAEs by System Organ Class (SOC) and Preferred Term (PT)
- TEAEs by Oral/Non-Oral and PT
- Treatment emergent treatment related AEs by Oral/Non-Oral and PT
- Treatment emergent treatment related serious AEs by SOC and PT

Separate listings will be presented for:

- Deaths, SAEs and any AEs leading to product or study discontinuation.
- OST findings (with a summary of abnormalities by visit)
- OHT findings (with a summary of changes by visit)
- Exposure to study product ([Section 12.3.6.1.](#))

Medical device incidents will be listed; if there are no incidents, a null listing will be produced. While no specific risks or anticipated adverse device effects are expected from use of the medical device (manual toothbrush) provided, any medical device incidents reported during the conduct of this study will be assessed to evaluate the safety of the device.

Property of Haleon- Confidential

May not be used, divulged, published or otherwise disclosed without the consent of Haleon

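### Treatment emergence is defined by onset timing alone, so an acclimatization-period AE that worsens on the investigational toothpaste and stays on its original record is missing from every TEAE table and TEAE-only listing

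*SAP*

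**What the plan says.** SAP 4.5.1 gives the inclusion rule: "Treatment emergent adverse events (TEAEs) are defined as new AEs that occur on or after the first study product use". It then gives the exclusion rule: "AEs with an onset date/time prior to the first study product use will be considered as non-treatment emergent". No exception is made for an earlier event that later worsens or becomes serious.

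Protocol 12.3.4 regards an AE as treatment emergent "if they occur on or after the first use of investigational product at Baseline (Visit 2"). It is also silent on worsening. It has two provisions that SAP 4.5.1 does not repeat. One concerns undated events: "In the event of a missing start date, an AE will be assumed to be" treatment emergent unless its end date falls before treatment began. The other is a listing of any AE that led to product or study discontinuation, with no TEAE restriction.

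On collection, Protocol 10.3 says: "All AEs, and therefore all SAEs, will be collected from immediately after a subject provides consent to participate in the study". On follow-up of an AE already reported, Protocol 10.6 says: "New or updated information will be recorded in the AE section of the eCRF and on the SAE form", as the classification of the event requires. Neither section says whether a worsening opens a new record or updates the old one.

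**The concern.** TEAEs are the only safety endpoint in the objectives tables (Protocol 3, SAP 1.2), and every planned AE summary by study product is a TEAE table. The comparison between arms on tolerability therefore depends on what qualifies as treatment emergent.

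The design makes pre-treatment AEs likely to be on the database. Subjects use a different toothpaste for 14-28 days, AEs are elicited after the first acclimatization brushing and again at Baseline (Protocol 8.1.7.1 and 8.2.1.2), and AEs are followed until they resolve or stabilize. A mild oral irritation that starts in acclimatization and becomes severe on the assigned paste is a tolerability signal for that paste. Protocol 2.1 describes a modified abrasive system and a new flavor in the Test Toothpaste, so aggravation of existing oral complaints is a fair question to ask of it. An onset-only rule can hide that answer from the by-arm counts, and any shortfall would fall more heavily on whichever product aggravates more.

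**Working it through.** The plan states no figure on this point to reproduce. The check is a reading of the rules, plus one short calculation to size the pre-treatment window.

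**1. Can an AE be open at first investigational use?** Yes. Collection starts at consent (Protocol 10.3), acclimatization lasts 14-28 days (Protocol 1.1), and AEs are followed to resolution or stabilization (Protocol 10.6).

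**2. How much of AE collection time comes before treatment?** Inputs: acclimatization 14 to 28 days; treatment 56 ± 3 days, so 53 to 59 days; then 5 days after last use (Protocol 10.3).
- Smallest share: 14 / (14 + 59 + 5) = 14/78 = 18%.
- Largest share: 28 / (28 + 53 + 5) = 28/86 = 33%.

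These are shares of calendar time. They show that the window is not trivial, and say nothing about how many AEs start in it, remain open and then worsen.

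**3. Trace one event.** Take an AE with onset in acclimatization that worsens after first use of the investigational toothpaste. Its fate under SAP 4.5.1 depends on how the site records the worsening:

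| Display | TEAE only? | One record, original onset | New record, on-treatment onset |
|---|---|---|---|
| Tables 14.3.1.1, 14.3.1.2 | Yes | Absent | Counted |
| Tables 14.3.1.3, 14.3.1.4 (treatment related) | Yes | Absent | Counted if related |
| Listing 14.3.2.3 (discontinuation) | Yes | Absent, even if it caused withdrawal | Listed if it led to discontinuation |
| Listing 14.3.2.4 (oral) | Yes | Absent, even if oral | Listed if oral |
| Listings 14.3.2.1, 14.3.2.2 (deaths, non-fatal SAEs) | No | Listed if fatal or serious | Listed if fatal or serious |
| Listing 16.2.7.1 (all AEs) | No | Listed | Listed |

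**4. Do the recording rules decide between the last two columns?** No.
- Protocol 10.1 treats exacerbation of a chronic or intermittent pre-existing condition as an AE, which points to a new record.
- Protocol 9.3.1 and 9.3.2 make a soft- or hard-tissue finding that worsens an AE, but the comparison is with Screening. An abnormality first seen at Visit 2, before the first investigational brushing, is already an AE with pre-treatment onset. No rule separates its later deterioration.
- Protocol 10.6 speaks of entering updated information, which points to the existing record.

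**5. Does the soft-tissue summary fill the gap?** Only partly. Table 14.3.4.1 counts subjects with abnormalities, without abnormalities or not examined, by visit and product. A finding that goes from abnormal to worse stays in the same cell.

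**6. Which product is the anchor?** SAP 4.5.1 refers to first study product use. Protocol 6.1 and SAP Table 1-3 include the acclimatization toothpaste among the study products. The SAP's fallback to the randomization date and the wording of Protocol 12.3.4 show that the investigational toothpaste is meant, but SAP 4.5.1 does not say so.

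**7. SAP against protocol.** SAP 4.5.1 omits the missing-start-date rule and limits the discontinuation listing to TEAEs, while SAP 5 reports no changes from the protocol's planned analysis.

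**The case against.** The strongest reply is that the protocol already makes worsening reportable. Exacerbation of a pre-existing condition meets the AE definition, worsened oral findings must be recorded as AEs, and soft-tissue examinations take place at every visit from Baseline onward. A worsening recorded in that way with on-treatment onset is a new AE and enters the tables. A convention on records could also sit in an eCRF completion guideline, which is not among the documents. This stands, and it makes the effect conditional. A reader might infer that every acclimatization AE that worsens is lost; the documents do not support that. They leave the outcome to site practice, so the same clinical course can be counted for one subject and not for another.

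Secondly, serious events do not disappear. The death, non-fatal SAE and all-AE listings carry no TEAE restriction. This also stands: the loss is from the by-arm counts and the two TEAE-only listings, and the event remains in the report.

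Thirdly, the affected set may be small. Eligibility is reviewed again at Baseline after an oral examination (Protocol 8.2.1.5 and 8.2.1.7), and Protocol 2.2 describes adverse reactions to 5% CSPS toothpaste as rare or very rare. The 18-33% might be read as a share of AEs, which it is not.

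Finally, someone might infer that the SAP classes undated AEs as non-emergent. It does not: its exclusion applies to an onset before first use, and SAP 5 does not revoke the protocol rule. That omission is a minor wording gap.

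**Conclusion.** The point holds in conditional form. If an AE starts in acclimatization, is kept as one record with its original onset date, and increases in intensity or becomes serious after first use of the investigational toothpaste, the stated rule omits it from all four TEAE tables and from Listings 14.3.2.3 and 14.3.2.4. This follows from an explicit rule in SAP 4.5.1, and the recording instructions do not prevent it.

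The frequency cannot be estimated, because the documents give no AE rates and no rate of worsening. The conclusion assumes that no convention outside these documents already requires a new record for each worsening. The primary endpoint, significance level, sample size and efficacy analyses are unaffected. The omitted missing-start-date rule and the narrowed discontinuation listing are SAP-protocol mismatches whatever the recording practice; the first is minor.

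**What to change.** 1. In Protocol 12.3.4 and SAP 4.5.1, define a TEAE as an AE with onset on or after first use of the investigational toothpaste, or an AE with earlier onset that increases in intensity or becomes serious on or after that use. Name the investigational toothpaste as the anchor in SAP 4.5.1.
2. Choose one recording mechanism and state it in the SAP and the eCRF instructions. Either open a new record with its own onset date and leave the original non-emergent, or keep the original record and add a flag with the date of worsening. Doing both would turn one worsening into two events in the number of distinct AEs that Protocol 12.3.4 reports.
3. Carry the protocol's missing-start-date rule into SAP 4.5.1.
4. Widen Listing 14.3.2.3 to any AE leading to product or study discontinuation, as Protocol 12.3.4 specifies.

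The cost is a few lines in the protocol and SAP and one line of eCRF guidance, settled before unblinding. The downside is that TEAE counts may rise slightly in both arms.
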